# 9.6.2 Statistical Methods for Safety Analyses

The analysis of safety results will follow a tiered approach (Table 6). The tiers differ with respect to the analyses that will be performed. AEs (specific terms as well as system organ class terms) and events that meet predefined limits of change (PDLCs) in laboratory and vital sign parameters are either pre-specified as "Tier 1" endpoints, or will be classified as belonging to "Tier 2" or "Tier 3" based on the number of participants with events.

#### Tier 1 events

Safety parameters or AEs of special interest that are identified a priori (see Section 9.4.2) constitute "Tier 1" safety endpoints that will be subject to inferential testing for statistical significance with p-values and 95% CIs to be provided for between-treatment differences in the proportion of participants with events; these analyses will be performed using the unstratified Miettinen and Nurminen method.

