## 6.3 Measures to Minimize Bias: Randomization and Blinding

#### 6.3.1 Intervention Assignment

Intervention randomization will occur centrally using an IRT system. There are 2 study intervention arms. Participants will be assigned randomly in a 1:1 ratio to suvorexant and placebo, respectively.

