#### 6.3.2 Stratification

Intervention randomization will be stratified according to the following factors:

1. Hospitalization reason (acute disease, elective surgery)

If either the proportion of participants hospitalized due to acute disease or those hospitalized due to elective surgery exceeds approximately 60% of the total targeted sample size, the remaining participants will only be enrolled into the other stratum within this stratification factor.

2. Age category (<75 years,  $\geq 75$  years)

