#### Primary endpoint

The treatment difference in the proportion of participants with delirium during the assessment period as assessed by DSM-5, along with the corresponding 95% CI and the p-value based on the Miettinen and Nurminen method, will be provided. The analysis will be stratified by hospitalization reason (acute disease, elective surgery) and age category (<75 years,  $\geq$ 75 years). The Cochran-Mantel-Haenszel weight will be used to obtain stratum-adjusted proportion difference.

Missing assessments will be considered not having delirium. A supportive analysis using survival analytic methods will be conducted to assess the robustness of the conclusion from the primary analysis to the assumption about the missing assessment of delirium. Details will be described in the sSAP.

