#### Tier 2 events

Tier 2 parameters will be assessed via point estimates with 95% CIs provided for differences in the proportion of participants with events (also via the unstratified Miettinen and Nurminen method).

Membership in Tier 2 requires that at least 4 participants in any treatment group exhibit the event. The threshold of at least 4 events was chosen because the 95% CI for the between-group difference in percent incidence will always include zero when treatment groups of equal size each have less than 4 events and thus would add little to the interpretation of potentially meaningful differences. Because many 95% confidence intervals for Tier 2 events may be provided without adjustment for multiplicity, the CIs should be regarded as a helpful descriptive measure to be used in review, not a formal method for assessing the statistical significance of the between-group differences in adverse events and safety parameters that meet predefined limits of change.

In addition to individual events that occur in 4 or more participants in any treatment group, the broad AE categories consisting of the proportion of participants with any AE, a drug related AE, a serious AE, an AE which is both drug-related and serious, and discontinuation of study medication due to an AE will be considered Tier 2 endpoints.

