#### 9.10 Subgroup Analyses

To determine whether the treatment effect is consistent across various subgroups, the estimate of the between-group treatment effect (with a nominal 95% CI) for the primary endpoint will be estimated for the following subgroups using the unstratified Miettinen and Nurminen method.

- Hospitalization reason (acute disease, elective surgery)
- Age category (<75 years,  $\geq$ 75 years)

Additional subgroup analyses will be described in the sSAP.

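### The broad Tier 2 adverse event comparisons ignore the randomisation strata, so their descriptive intervals are somewhat wider than needed if event rates differ between acute-disease and elective-surgery participants

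*Combined protocol and SAP*

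**What the plan says.** Section 6.3.2 states "Intervention randomization will be stratified according to the following factors": hospitalization reason and age category. It closes a hospitalization-reason stratum once its share "exceeds approximately 60% of the total targeted sample size". Section 6.3.1 sets 1:1 allocation. Section 9.6.1 analyses the primary endpoint by the Miettinen-Nurminen method stratified by both factors: "The Cochran-Mantel-Haenszel weight will be used to obtain stratum-adjusted proportion difference".

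Section 9.6.2 handles safety without strata. For Tier 1, "these analyses will be performed using the unstratified Miettinen and Nurminen method". Tier 2 gets point estimates and 95% intervals, "also via the unstratified Miettinen and Nurminen method". The five broad AE categories are placed in Tier 2 whatever their count; a specific AE term enters Tier 2 when at least 4 participants in an arm have it. Table 6 gives Tier 2 no p-value, and the text says "the CIs should be regarded as a helpful descriptive measure to be used in review, not a formal method for assessing the statistical significance". Table 8 (Section 9.9.2) sets out detectable AE differences for 100 per arm, also without strata. No reason is given for leaving the strata out, and no stratified safety analysis is described.

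**The concern.** When allocation is balanced within strata, the difference between arms carries little of the variation between strata. An unstratified variance still counts that variation, so the interval is too wide when the strata have different event rates.

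Different rates are plausible here, though not documented. Acute-disease participants enter with APACHE II 8-30 or ECOG PS 3-4; the others come for scheduled surgery under general anesthesia (Section 5.1). Safety is a primary objective (Section 3), and for harm a wide interval is not cautious: it makes a real difference harder to see.

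There is also a small inconsistency. DSM-5 delirium must be recorded as an AE (Sections 8.2.1 and 8.4.6), so it counts towards any AE. Because it also forces discontinuation (Section 7.1), it may count towards discontinuation due to an AE, depending on how the reason is coded. At the planned 30% placebo rate, 4 or more cases in that arm is near certain, so delirium will be a Tier 2 term in its own right. Largely the same event would then be reported stratified as efficacy and unstratified as safety, although the analysis population and reporting window also differ.

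**Working it through.** **1. The plan's own safety figures.** Table 8, last row: 49.3% versus 30.0%, 100 per arm, two-sided 5%. The pooled rate is 0.3965.
- Null SE = √(2 × 0.3965 × 0.6035 / 100) = 0.0692.
- Alternative SE = √(0.493 × 0.507/100 + 0.30 × 0.70/100) = 0.0678.
- Power = Φ[(0.193 − 1.96 × 0.0692) / 0.0678] = Φ(0.846) = 80.1%.

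The six rows give 79.7, 80.1, 79.9, 79.7, 79.8 and 80.1%. Table 8 is correct for an unstratified comparison.

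**2. Inputs for the comparison.** From the documents: 100 per arm, 1:1 allocation, and a hospitalization-reason mix between roughly 40/60 and 60/40 (Section 6.3.2). Assumed: event rates by stratum, no treatment difference, and exact balance within strata.

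**3. Formulas.** With stratum rates p_k, n_k per arm, weight w_k = n_k/100 (the CMH weight under 1:1) and overall rate p, the variances at zero difference, with the Miettinen-Nurminen N/(N−1) factor, are:
- Unstratified: 2p(1−p)/100 × 200/199.
- Stratified: Σ w_k² × 2p_k(1−p_k)/n_k × 2n_k/(2n_k−1).

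Example: 30% and 70%, 50 per arm in each stratum.
- Unstratified SE = √(2 × 0.25/100 × 200/199) = 0.0709.
- Stratified SE = √(2 × 0.25 × 2 × 0.21/50 × 100/99) = 0.0651.
- Ratio 0.919.

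The full score interval re-estimates the variance at each limit, so its gain is slightly smaller (ratio 0.925).

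**4. Full Miettinen-Nurminen 95% intervals on expected counts**, stratified by hospitalization reason only, 50/50 mix:

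| Rates in the two strata | Unstratified width | Stratified width | Change |
|---|---|---|---|
| 50% / 50% | 0.2752 | 0.2759 | +0.3% |
| 5% / 15% | 0.1755 | 0.1760 | +0.3% |
| 40% / 60% | 0.2752 | 0.2708 | −1.6% |
| 20% / 40% | 0.2540 | 0.2494 | −1.8% |
| 35% / 65% | 0.2752 | 0.2642 | −4.0% |
| 15% / 45% | 0.2540 | 0.2429 | −4.4% |
| 30% / 70% | 0.2752 | 0.2546 | −7.5% |
| 10% / 50% | 0.2540 | 0.2338 | −8.0% |

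A 60/40 mix gives nearly the same: −1.6% (40/60), −3.9% (35/65) and −7.2% (30/70).

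**5. Coverage at zero difference.** By exact enumeration (50/50 mix), the unstratified interval covers 94.9% (40/60), 95.6% (20/40), 95.5% (35/65), 96.2% (15/45), 96.3% (30/70) and 97.1% (10/50). The stratified interval, simulated in the same cases, stays between 94.9 and 95.1%. Over-coverage is therefore consistent from 30 points upward; at 20 points it is within the discreteness of the counts.

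**6. Using both factors instead (four strata of 25 per arm).** Equal rates cost about 0.8%; 40/60 gains 1.1%; 30/70 gains 7.0%. Adding age brings no benefit in these cases, where rates differ by one factor only.

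**7. Subgroups.** Take 50 per arm and 30% versus 11.6%, stratified by the remaining factor. The width goes from 0.3156 to 0.3173 (equal rates), 0.3153 (two-fold contrast) or 0.3127 (three-fold). The change is 1% or less.

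**The case against.** The case for leaving the plan alone is substantial, and most of it stands.

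- **The effect is conditional.** A reader might infer that intervals for all common events are too wide. The documents give no AE rates by stratum. With equal rates, or at 5% versus 15%, stratifying makes the interval marginally wider.
- **No planned test is affected.** A reader might infer that a safety test runs below its nominal 5% level. The broad categories are Tier 2, which has no p-value and whose intervals are declared descriptive. Only Tier 1 is tested, and for rare terms stratifying gains nothing.
- **The plan does not promise more precision than it delivers.** Table 8 is unstratified and reproduces as such.
- **Subgroups gain nothing useful.** Each Section 9.10 subgroup already fixes one stratification factor, and adjusting for the other changes the width by 1% or less.
- **The threshold of 4 fits the unstratified method.** With 100 per arm, 3 events versus 0 gives −0.8 to 8.5 points, and 4 versus 0 gives 0.2 to 9.9. Under stratification by both factors, three events in one very small stratum could exclude zero: 3/5 versus 0/5 gives z = 0.6/√(2 × 0.3 × 0.7/5 × 10/9) = 1.96. That is an extreme case, but the age split is not controlled.

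This does not remove the narrow point. The broad categories are in Tier 2 regardless of the threshold. The 60% limit keeps each hospitalization-reason stratum at roughly 40 or more per arm, so sparse strata do not arise. The possible gain, up to 8% in the cases examined, is far larger than the 0.3% cost.

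**Conclusion.** The point holds as a minor matter of precision and consistency, limited to the five broad Tier 2 AE categories and delirium recorded as an AE. Its size depends wholly on how far event rates differ by hospitalization reason: nothing if they are alike, about 2% of interval width at 20 points, 4% at 30 and 7-8% at 40. In absolute terms, at a 50% overall rate and a 40-point contrast, the interval shrinks from 27.5 to 25.5 percentage points. A category that turns out infrequent, as drug-related serious AEs may, will show no gain. The unstratified choice is clearly prespecified, any loss of accuracy is towards over-coverage, and no stated figure needs correcting. The documents do not support extending the point to Tier 1 terms, to type I error or to the subgroup estimates.

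**What to change.** In Section 9.6.2, state that the differences and 95% intervals for the five broad Tier 2 AE categories, and for delirium recorded as an AE, will use the Miettinen-Nurminen method with CMH weights stratified by hospitalization reason. Keep the unstratified method for Tier 1, for all other specific AE terms and the 4-participant rule, and for Section 9.10.

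The method is already specified for the primary endpoint, so the work is one or two sentences and a change to a few table rows. No primary hypothesis or related method is touched, so under the opening of Section 9 the change could be documented in the sSAP before database lock. The costs are an interval about 0.3% wider if rates do not differ between the strata, and two methods in the safety tables, which a footnote should identify.

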#### Tier 2 events

Tier 2 parameters will be assessed via point estimates with 95% CIs provided for differences in the proportion of participants with events (also via the unstratified Miettinen and Nurminen method).

Membership in Tier 2 requires that at least 4 participants in any treatment group exhibit the event. The threshold of at least 4 events was chosen because the 95% CI for the between-group difference in percent incidence will always include zero when treatment groups of equal size each have less than 4 events and thus would add little to the interpretation of potentially meaningful differences. Because many 95% confidence intervals for Tier 2 events may be provided without adjustment for multiplicity, the CIs should be regarded as a helpful descriptive measure to be used in review, not a formal method for assessing the statistical significance of the between-group differences in adverse events and safety parameters that meet predefined limits of change.

In addition to individual events that occur in 4 or more participants in any treatment group, the broad AE categories consisting of the proportion of participants with any AE, a drug related AE, a serious AE, an AE which is both drug-related and serious, and discontinuation of study medication due to an AE will be considered Tier 2 endpoints.

#### Tier 3 events

Safety endpoints that are not Tier 1 or 2 events are considered Tier 3 events. Only point estimates by treatment group are provided for Tier 3 safety parameters.

#### Continuous safety measures

For continuous measures such as changes from baseline in laboratory and vital sign parameters, summary statistics for baseline, on-treatment, and change from baseline values will be provided by treatment group in table format.

Safety Tier	Safety Endpoint	p-Value	95% CI for Treatment Difference	Descriptive Statistics
Tier 1	Complex sleep-related behaviors			
	Sleep paralysis (including sleep onset paralysis [adjudicated])			
	Hypnagogic or hypnopompic hallucinations			
	Somnolence resulting in discontinued intervention	Х	Х	Х
	Falls (adjudicated to rule out cataplexy)			
	Suicidal ideation and/or behaviors			
	Selected events associated with potential for abuse			
	Cataplexy (adjudicated)			
Tier 2	Any AE †			
	Any drug-related AE			
	Any serious AE			
	Any drug-related serious AE		Х	Х
	Discontinuation of study medication due to AE			
	Specific AEs, SOCs, or PDLCs (incidence $\geq 4$			
	participants in at least one of the treatment groups)			
Tier 3	Specific AEs, SOCs or PDLCs ‡ (incidence <4			
	participants in all of the treatment groups)			Х
	Change from Baseline Results (Labs, Vital Signs)			
	tes broad AE category of the number of participants re			
‡ Includ	es only those endpoints not pre-specified as Tier 1 or :	not already p	pre-specified as Tier 2	endpoints

Table 6Analysis Strategy for Safety Parameters

#### 9.6.3 Summaries of Baseline Characteristics, Demographics, and Other Analyses

The comparability of the treatment groups for each relevant demographic and baseline characteristic will be assessed by the use of tables and/or graphs. No statistical hypothesis tests will be performed on these characteristics. The number and percentage of participants screened and randomized, and the primary reasons for screening failure and discontinuation will be displayed. Demographic variables, baseline characteristics, primary and secondary diagnoses, and prior and concomitant therapies will be summarized by treatment either by descriptive statistics or categorical tables.

#### 9.7 Interim Analyses

There are no planned interim analyses for this study.

#### 9.8 Multiplicity

No multiplicity adjustment is planned as the study has a single primary hypothesis that will be addressed with a single comparison of two treatments using one endpoint.

### 9.9 Sample Size and Power Calculations

## 9.9.1 Sample Size and Power for Efficacy Analyses

A total of 200 participants will be randomized to suvorexant or placebo in a 1:1 ratio. The study will have a power of 90% with a two-sided significance level of 0.05 to detect a difference between treatments if the true proportion of participants with delirium in the suvorexant group is 11.6 % compared to 30% in the placebo group. The power will be 80% if the true proportion in the suvorexant group is 13.7%. If there are occurrences of delirium after randomization but prior to the first dose of study medication, then the number of randomized participants will be increased to account for such participants.

Previous researches show that delirium was observed at least in 10% - 20% of elderly hospitalized patients hospitalized for surgery or internal diseases (See Section 2). Since this study will enroll participants with higher risk of delirium than the general elderly hospitalized patients, it is anticipated that the incidence of delirium will be greater and the true proportion of participants with delirium is assumed to be 30% in the placebo group. Furthermore, the studies which prospectively assessed the treatment effect of suvorexant for delirium prevention [Azuma K, et al. 2018] [Hatta K, et al. 2017] resulted in treatment differences of ~17% - 18% versus the control group, and it is assumed that this study will have a similar treatment effect.

The table below provides true proportions of participants with delirium in the suvorexant group required to provide 90 (80) % power, under varying assumptions for the true proportion of participants with delirium in the placebo group.

Table 7True Proportion of Participants With Delirium in the Suvorexant and PlaceboGroups Required to Provide 90 (80) % Power (N =100 / arm)

% delirium in Placebo	% delirium in MK-4305 required to provide 90 (80) % Power		
25%	8.1% (10.0%)		
30%	11.6% (13.7%)		
35%	15.3% (17.6%)		
40%	19.2% (21.8%)		
45%	23.4% (26.1%)		
50%	27.8% (30.6%)		
Farrington and Manning method, α=0.05 (two-sided)			

## 9.9.2 Sample Size and Power for Safety Analyses

Table 8 summarizes the percentage point differences between the 2 treatment groups that could be detected with ~80% probability for a variety of hypothetical underlying incidences of an adverse event. These calculations assume 100 participants in each group and are based

on a 2-sided 5% alpha level. The calculations are based on an asymptotic method proposed by Farrington and Manning [Farrington CP, et al. 1990], with no multiplicity adjustments.

Incidence of A	Risk Difference			
Suvorexant (%)	Placebo (%)			
(N =100)	(N =100)	Percentage Point		
7.7	0.1	7.6		
12.1	2.0	10.1		
17.4	5.0	12.4		
24.9	10.0	14.9		
37.8	20.0	17.8		
49.3	30.0	19.3		
Based on an asymptotic method proposed by Farrington and Manning, $\alpha$ =0.05 (two-sided)				

Table 8Differences in Incidence of Adverse Events Between the 2 Treatment GroupsThat Can be Detected With an  $\sim 80\%$  Probability (N =100 / arm)

#### 9.10 Subgroup Analyses

To determine whether the treatment effect is consistent across various subgroups, the estimate of the between-group treatment effect (with a nominal 95% CI) for the primary endpoint will be estimated for the following subgroups using the unstratified Miettinen and Nurminen method.

- Hospitalization reason (acute disease, elective surgery)
- Age category (<75 years,  $\geq$ 75 years)

Additional subgroup analyses will be described in the sSAP.

## 9.11 Compliance (Medication Adherence)

Participants are to take 1 tablet of study medication per day. A day within the study will be considered an "On-Therapy" day if the participant takes 1 tablet of study medication. The "Number of Days Should be on Therapy" is the total number of days from randomization to the last scheduled day for treatment administration for that participant [which is the day before the last assessment visit (Visit 4)].

For each participant, percent compliance will then be calculated using the following formula:

 $PercentCompliance = \frac{Number of Days on Therapy}{Number of Days Should be on Therapy} \times 100.$ 

Summary statistics will be provided on percent compliance by treatment group for the FAS population.

# 9.12 Extent of Exposure

The distribution of the number of participants with respect to the number of days on study medication will be tabulated by treatment for the APaT population.

#### 10 SUPPORTING DOCUMENTATION AND OPERATIONAL CONSIDERATIONS

#### 10.1 Appendix 1: Regulatory, Ethical, and Study Oversight Considerations

#### **10.1.1** Code of Conduct for Clinical Trials

#### Merck Sharp & Dohme LLC, Rahway, NJ, USA (MSD)

#### **Code of Conduct for Interventional Clinical Trials**

#### I. Introduction

#### A. Purpose

MSD, through its subsidiaries, conducts clinical trials worldwide to evaluate the safety and effectiveness of our products. As such, we are committed to designing, implementing, conducting, analyzing, and reporting these trials in compliance with the highest ethical and scientific standards. Protection of participants in clinical trials is the overriding concern in the design and conduct of clinical trials. In all cases, MSD clinical trials will be conducted in compliance with local and/or national regulations (including all applicable data protection regulations), and International Council for Harmonisation Good Clinical Practice (ICH-GCP), and also in accordance with the ethical principles that have their origin in the Declaration of Helsinki.

#### B. Scope

Highest ethical and scientific standards shall be endorsed for all clinical interventional investigations sponsored by MSD irrespective of the party (parties) employed for their execution (e.g., contract research organizations, collaborative research efforts). This Code is not intended to apply to trials that are observational in nature, or which are retrospective. Further, this Code does not apply to investigator-initiated trials, which are not under the full control of MSD.

#### II. Scientific Issues

#### A. Trial Conduct

#### 1. Trial Design

Except for pilot or estimation trials, clinical trial protocols will be hypothesis-driven to assess safety, efficacy and/or pharmacokinetic or pharmacodynamic indices of MSD or comparator products. Alternatively, MSD may conduct outcomes research trials, trials to assess or validate various endpoint measures, or trials to determine patient preferences, etc.

The design (i.e., participant population, duration, statistical power) must be adequate to address the specific purpose of the trial. Participants must meet protocol entry criteria to be enrolled in the trial.

#### 2. Site Selection

MSD selects investigative sites based on medical expertise, access to appropriate participants, adequacy of facilities and staff, previous performance in clinical trials, as well as budgetary considerations. Prior to trial initiation, sites are evaluated by MSD personnel (or individuals acting on behalf of MSD) to assess the ability to successfully conduct the trial.

